**SHW and PBMT Arm**

This treatment arm will receive both SWT and PBMT in addition to the physical therapy program from [name]. The SWT will be performed by PI, [name], and the PBMT will be performed by either the PI or a trained member of the study staff. Training for the PBMT will be conducted by a local LightForce representative. They will receive PBMT using the LightForce® XPi 25W device with the Smart Hand Piece technology, which has a built-in accelerometer in the hand piece that controls the speed of light delivery to the treatment area. The therapy is delivered through a flexible optical fiber threaded through the hand piece, which contains a rolling glass massage ball. PBMT will be delivered at 10 J/cm^2 and applied in a serpentine pattern to the calf from the fold in the back of the knee to the bottom of the foot and the sole of the foot including the arch. A member of the study team will calculate the treatment area according to a standard protocol (appendix I), and calculate the treatment time. Patients will receive PBMT twice a week for three weeks, and SWT will be combine once a week for three weeks.

**b. Visit Details**

After consent has been obtained, patients will be randomly allocated to one of the three treatment arms. The expectations for the visits for the different study arms are outlined below:

Table 1: Outlined visits from three different study arms

	Physical Therapy only	Shockwave	PBMT & Shockwave
T0: Baseline	Subject screening & enrollment*		
Part 1	Subject to be randomly assigned a treatment arm		

T1: week 1 visit 1	VISA-A, ProMIS-29, UWRI, patient goals Ultrasound, heel raises & hopping test	Treatment 1 VISA-A, ProMIS-29, UWRI, patient goals Ultrasound, heel raises & hopping test	PBMT & SW treatment VISA-A, ProMIS-29, UWRI, patient goals Ultrasound, heel raises & hopping test
T2: week 1 visit 2	telephone check-in	telephone check-in	PBMT treatment only
T3: week 2 visit 1	telephone check-in	Treatment 2	PBMT & SW treatment
T4: week 2 visit 2	telephone check-in	Telephone check-in	PBMT treatment only
T5: week 3 visit 1	telephone check-in	Treatment 3	PBMT & SW treatment
T6: week 3 visit 2	telephone check-in VISA-A, ProMIS-29, UWRI	telephone check-in VISA-A, ProMIS-29, UWRI	PBMT treatment only VISA-A, ProMIS-29, UWRI
T7: 6 week follow up	telephone check-in VISA-A, ProMIS-29 & UWRI	telephone check-in VISA-A, ProMIS029 & UWRI	telephone check-in VISA-A, ProMIS-29 & UWRI
T8: 3 month follow up	VISA-A, ProMIS-29, UWRI, patient goals, patient satisfaction, new treatment selection Ultrasound, heel raise & hopping test	VISA-A, ProMIS-29, UWRI, patient goals, patient satisfaction, new treatment selection Ultrasound, heel raise & hopping test	VISA-A, ProMIS-29, UWRI, patient goals, patient satisfaction, new treatment selection Ultrasound, heel raise & hopping test
Part 2	Participants to choose treatment and follow visit schedule as listed above		
T9: 6 month follow up	Patient satisfaction, ultrasound, heel raises & hopping test	Patient satisfaction, ultrasound, heel raises & hopping test	Patient satisfaction, ultrasound, heel raises & hopping test

\*At baseline subjects will be screened for their eligibility using the inclusion and exclusion criteria described on page 2 of this document. To determine pregnancy female patients will be asked if they are pregnant, **planning to become pregnant**, or not **pregnant**. MGB guidelines state that when using non-iodizing radiation if a woman states she is not pregnant, no pregnancy test is required.

Due to the nature of COVID-19, in-person visits, check-ins, and questionnaires, can be rescheduled +/- 14 days within each of the outlined study timepoints.

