**V. STUDY PROCEDURE**

**a. Overall Research Design and Methods**

This study has been split into two parts. **Part 1 is the initial randomized control trial, and Part 2 is when the participants can select the treatment they want to receive if they are not satisfied with their initial treatment.** In Part 1 patients will not be blinded to the treatment arm that they receive due to the obvious differences in the treatments.

Participants will also be asked to log their return to running at home using the University of Delaware Return to Sport protocol.

*Part 1*

Study participants will be randomly assigned to one of three treatment groups, using a block randomization generator **that is implemented into REDCap**. There will be 20 patients per treatment group, no power calculation as this is a feasibility study. The three treatment arms are: physical therapy only, SWT and physical therapy, and a combination of SWT, PBMT and physical therapy. All runners, regardless of treatment group, will be asked to enroll in physical therapy at a location that is convenient to them (and accepts their insurance if applicable) and complete a standard physical therapy program addressing individual strength deficits in both proximal (spine and hip girdle) along with distal (thigh, leg and foot/ankle) muscle groups. To standardize loading program, we will provide all runners with an at-home exercise program designed by [name] for progressive Achilles tendon loading. This will be

completed alongside the physical therapy they are receiving. Activities including running will be allowed as tolerated following published guidelines by [name].

In subjects who have bilateral AT, the leg with the most severe symptoms (determined by the VISA-A) will be chosen as the primary data for the study, however both legs will be treated consistent with the treatment group the subject was randomized into. Outcomes will be obtained for each Achilles tendon, regardless of treatment, using VISA-A at each data collection point. Participants will also be asked to complete a weekly log of running and completing PT exercises.

## Part 2

At the 3-month follow-up, participants who are not satisfied with their outcome will be given the option to choose one of the remaining treatment arms. Regardless of what treatment a patient chooses, if any, there will be one final visit conducted at 6 months for final data collection.

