### **Physical Therapy**

In part 1 the physical therapy only arm will only have to complete 2 in-person visits, baseline and the 3 month follow up, but they will receive two calls a week for the first three weeks to ensure consistency with the other treatment arms, and the virtual 6 week follow-up. The number of visits they will have to complete in part 2 will depend on which treatment arm the subject selects, but they will be required to come in at least once to complete the 6 month follow-up. The study will start when they enroll in the study and start the [name] protocol.

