### **Study Visits for all treatment arms:**

An overview of the questionnaires and measurements that will be taken at various time points, regardless of treatment arm, are described in table 2.

Table 2: Overview of questionnaires and measurements required regardless of treatment arm

Visit	Questionnaires							Measurements	
	VISA-A	ProMIS-29	UWRI	Patient goals	Treatment preference	Patient satisfaction	Return to sports worksheet collection	Ultrasound	Heel raise & hopping test
Baseline	x	x	x	x	x			x	x
3-week follow-up	x	x	x				x		
6-week follow up	x	x	x				x		
3-month follow-up	x	x	x	x	x	x	x	x	x
6-month follow up	x	x	x	x	x	x	x	x	x

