## **VI. BIOSTATISTICAL ANALYSIS**

### **a. Specific data variables being collected**

#### *Questionnaires:*

- Symptoms severity specific to Achilles will be **VISA-A**

- The VISA-A is currently the only valid and reliable measure to assess function and pain in AT (validity,  $P < 0.01$ ; test-re-test reliability,  $r = 0.98$ ) (2\*)
- ProMIS-29 will be used to capture other aspects of non-disease specific measures of health-related domains (physical, mental and social health).
- The University of Wisconsin Running Injury and Recovery Index (**UWRI**) will measure aspects unique to the running population.
- Visual analog scale of pain
- To quantify patient choice and motivation for treatment, an unvalidated survey will be obtained to determine patient goals of enrollment in study and reason for selecting a different intervention.
- Patient satisfaction with treatment
- **Participant demographics**
  - **Age at enrollment**
  - **Gender**
  - **Fitzpatrick skin type**
  - **Self-identified race and/or ethnicity**
  - **Marital status**
  - **Military status**
  - **Exclusion Criteria**
  - **BMI calculated from height and weight**
  - **Achilles tendon surgical history**
- **Expected AE interview forms**
  - **Achilles specific (one for each limb at week 1 check in, week 2 check in, 3 week follow-up, 6 week follow-up, 3 month follow-up, and 6 month follow-up)**

*Ultrasound:* Ultrasound measures will be assessed at baseline, 3 months and 6 months. Measures of interest include cross-sectional area, degree of thickening within the tendon at site of maximal circumference and maximal pain, and presence and number of neovessels on color flow doppler.

*Function:* Quantitative function in heel raises to fatigue will be measured at baseline, 3 months and 6 months on both affected and unaffected limb. We will also ask the participants to complete 20 hops and rate their pain using a visual analog scale (0 to 10).

*Return to running:* We will be asking participants to record their return to running, following Drs. Silbernagel & Crossley protocol. In order to log this, they will track the date, exercise and pain level using the University of Delaware training diary.

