### **c. Statistical methods**

For the statistical analysis of both the primary outcome, VISA-A, and secondary outcomes, PROMIS-29, UWRI, VAS, ultrasound measurements, and functional tests, we will use the

Shapiro-Wilk test to for normality in the data. For the continuous data we will use the t-test and ANOVA test if the data is normally distributed, and we will use the Mann-Whitney U test and Kruskal-Wallis analyze the data that is not normally distributed. For the binary data we will use the chi or Fishers test to compare the data.

In the first phase of the study, the randomized control trial, we will use a multivariable linear regression, controlling for: sex, BMI, age, medical condition (thyroid disease and diabetes) and prior oral steroid and/or fluoroquinolone use. In phase 2 after the elective cross-over, we will use the models described above as repeated measure models.

Interim analysis will be performed after 30 participants are enrolled to review for safety and tolerance to treatment.

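### Read literally, Table 1 gives interim Part 2 questionnaires to switchers only, while Table 2 gives them to nobody; the tables need reconciling and collection should not depend on the choice to switch

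*Combined protocol and SAP*

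**What the plan says.** Section II makes response to cross-over the secondary outcome. Section V.a (Part 2) says that at 3 months "participants who are not satisfied with their outcome will be given the option to choose one of the remaining treatment arms". It then adds: "Regardless of what treatment a patient chooses, if any, there will be one final visit conducted at 6 months for final data collection".

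Section V.b, Table 1, has a single Part 2 row: "Participants to choose treatment and follow visit schedule as listed above". The schedule above that row has VISA-A, PROMIS-29 and UWRI at T6 (week 3) and T7 (week 6) in all three arms. The arm-specific text after the table makes the number of Part 2 visits depend on the treatment chosen, with a floor of one. For the physical therapy arm, "they will be required to come in at least once to complete the 6 month follow-up".

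Table 2 is titled "Overview of questionnaires and measurements required regardless of treatment arm". Its rows are baseline, 3 weeks, 6 weeks, 3 months and 6 months.

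Section VI.c gives the Part 2 analysis in one sentence: "In phase 2 after the elective cross-over, we will use the models described above as repeated measure models". It names no time points, comparator or time origin.

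**The concern.** Taken at face value, Table 1 makes outcome collection between months 3 and 6 depend on the participant's own decision to switch, and that decision is open only to those dissatisfied at T8. Every interim Part 2 score would then come from a switcher.

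The protocol expects improvement in every arm, and the exercise programme runs to 6 months. Continued recovery is therefore a live alternative explanation for any gain in the first weeks after a switch. Without scores from people who stayed on their allocation, the data cannot show what the course over the same weeks looks like without a switch.

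Taken at face value, Table 2 removes the asymmetry but leaves the early response to a switch unmeasured. Site staff cannot follow both tables, and interim scores that are not collected cannot be recovered later.

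**Working it through.** The plan states no figure on this point and has no power calculation, so the check is a count of scheduled assessments.

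**Inputs.** Table 1 (Part 2 row, T6, T7, T9), Table 2, section V.a Part 2, the arm-specific visit text in V.b, and section VI.c. I take 3 months as about 13 weeks and 6 months as about 26.

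**Timing of the interim points.** 13 + 3 = week 16 and 13 + 6 = week 19. The repeated T1 falls at or near T8, and the repeated T8 at or near the 6-month visit, so neither adds an interim point. With the 14-day allowance in V.b the windows are weeks 14 to 18 and 17 to 21. They overlap between weeks 17 and 18, which is one reason the time origin has to be fixed.

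**Questionnaire sets strictly between months 3 and 6, per person**

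| Reading | Switcher | Non-switcher |
|---|---|---|
| Table 1, literal | 2 | 0 specified |
| Table 2, literal | 0 | 0 |
| Same points for everyone | 2 | 2 |

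**What this does to the model.** Suppose the Part 2 model has four time points (T8, +3 weeks, +6 weeks, 6 months) and a switch indicator. That gives 4 × 2 = 8 group-by-time means. With questionnaires at 6 months as in Table 2:
- Table 1 reading: 4 switcher cells + 2 non-switcher cells = 6 of 8 observed. At +3 and +6 weeks the time indicator and the time-by-switch term are the same column, because every record there belongs to a switcher. Only their sum can be estimated. A model without the interaction would still run, but its interim time effects would come from switchers alone.
- Table 2 reading: only T8 and 6 months exist, and 4 of 4 cells are observed. There is no aliasing, but no early response either.
- Same points for everyone: 8 of 8 observed.

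**Number of records.** The documents give no switch rate. Let k of the planned 60 switch, assuming full enrolment and completion. The Table 1 reading yields 2k interim sets, none from non-switchers. Equal collection yields 2 × 60 = 120, so 2 × (60 − k) are added: 80 if k = 20, 60 if k = 30, and between 0 and 120 over all k. Against the Table 2 reading, all 120 are new.

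**Related entries.** The adverse event form list, "week 1 check in, week 2 check in, 3 week follow-up, 6 week follow-up, 3 month follow-up, and 6 month follow-up", names no separate points after a switch, which fits Table 2 better than Table 1. Table 1's T9 row reads "Patient satisfaction, ultrasound, heel raises & hopping test" and omits the three questionnaires, while Table 2 marks all three at 6 months. The two tables therefore also differ at the 6-month visit.

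**The case against.** Several points on the other side have force.

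- Table 1 refers to a visit schedule and does not mention questionnaires in its Part 2 row. Table 2 and the adverse event list point the other way. A reader might infer that switchers definitely repeat the questionnaires; the documents leave this open. The row also spans all arms, so the exemption of non-switchers is an inference from the wording of V.a and the one-visit floor. This stands, and it is why reconciliation comes first.
- A reader might infer that switchers have no concurrent comparator of any kind. That is too broad. Participants who switch into different arms would share the repeated schedule and can be compared with each other, and everyone attends at 6 months. The weekly running and exercise log, which has no stated end, also covers everyone, although it does not replace VISA-A, PROMIS-29 or UWRI. What is missing is narrower: non-switcher scores at the interim points.
- Cross-over response can be read as within-person change, and the plan commits to no interim contrast of switchers with non-switchers. This is fair. The aliasing matters only if interim points enter the Part 2 model, which section VI.c neither says nor excludes.
- A reader might infer damage to the short-term shockwave question raised in section I. The documents do not support this: Part 1 is randomised and collects all three questionnaires in every arm at weeks 3 and 6.
- Equal collection does not make the groups comparable. Non-switchers will mostly be people satisfied at 3 months. This stands in full and limits what the fix can claim.

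**Conclusion.** The point holds in a narrow form. The tables conflict on whether questionnaires are collected between months 3 and 6. On the literal Table 1 reading the count is 2 sets per switcher against 0 specified per non-switcher, so time since T8 cannot be separated from switching at those two points. On the Table 2 reading it is 0 for both.

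This rests on two assumptions: that following the schedule again includes its questionnaires, and that the Part 2 model would use the interim scores. The size of any resulting bias cannot be stated, because the documents give neither a switch rate nor an expected course.

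The effect is confined to the non-randomised secondary phase of a pilot. The randomised comparison at 3 months is untouched, and so is the existence of a common 6-month visit. It is a desirable improvement and not a condition for the trial to proceed.

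**What to change.** 1. Reconcile Tables 1 and 2 for Part 2. State which questionnaires are collected from switchers and from non-switchers between months 3 and 6, and settle in the same amendment whether T9 includes VISA-A, PROMIS-29 and UWRI.
2. Collect these three questionnaires remotely from every participant, switcher or not, at the same 3- and 6-week points after T8. Add both rows to Table 2 and to the Part 2 block of Table 1.
3. In section VI.c, define the time origin (T8), the time points and the comparison in the Part 2 model. Record the start date of any new treatment, since it may fall after T8.
4. State that the contrast of switchers with non-switchers is non-randomised and confounded by dissatisfaction at 3 months, is descriptive, and is adjusted for the T8 score.

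The cost is a table amendment and up to two remote questionnaire sets per participant, with slightly more burden and some staff time to follow up non-response. Part 1 already pairs the 6-week questionnaires with a telephone contact in every arm. REDCap is in use for consent, randomisation and data sharing; that it can also deliver questionnaires is an assumption to confirm. The change should be in place before participants reach T8.

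If it is not made, report early change after a switch as within-person and descriptive only.

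### At 6 months Table 1 lists three of the nine assessments that Table 2 requires; followed literally, it leaves participants who do not switch with no VISA-A, PROMIS-29 or UWRI after month 3

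*Combined protocol and SAP*

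**What the plan says.** Section V.b contains two schedules. Table 1 goes visit by visit and arm by arm. Its T9 (6-month) row has the same entry in each of the three columns: "Patient satisfaction, ultrasound, heel raises & hopping test". Table 2 is titled "Overview of questionnaires and measurements required regardless of treatment arm", and its 6-month row is marked in all nine columns: VISA-A, PROMIS-29, UWRI, patient goals, treatment preference, patient satisfaction, return-to-sports worksheet, ultrasound, and heel raise with hopping. No sentence says which table takes precedence.

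The surrounding text helps only in part:

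- Section V.a, in the Part 1 paragraph on bilateral disease: "Outcomes will be obtained for each Achilles tendon, regardless of treatment, using VISA-A at each data collection point".
- Section V.a, Part 2: whatever a participant chooses, "there will be one final visit conducted at 6 months for final data collection". The items are not listed.
- Section VI.a dates the measurements: "Ultrasound measures will be assessed at baseline, 3 months and 6 months", and "Quantitative function in heel raises to fatigue will be measured at baseline, 3 months and 6 months on both affected and unaffected limb". It gives no dates for VISA-A, PROMIS-29 or UWRI.
- Section V.b on the physical therapy arm says of Part 2 that "they will be required to come in at least once to complete the 6 month follow-up".

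Section VI.c names VISA-A as the primary outcome, with PROMIS-29 and UWRI among the secondary outcomes, and plans repeated-measures versions of its models after the elective cross-over. Section II makes cross-over response the secondary outcome.

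**The concern.** The two tables give different instructions for the same visit, and the difference includes the primary outcome instrument. It is unlikely to be a fault of text extraction: the T9 entry is complete and identical in three cells, and the 3-month row (T8) above it spells out VISA-A, PROMIS-29, UWRI and patient goals.

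The possible loss is selective. Only participants dissatisfied at 3 months are offered a different treatment. Table 1 has those who take one go through the visit schedule again, and that schedule contains the questionnaires. Those who do not switch have only the 6-month visit. If staff work from Table 1, whether a participant has any Part 2 questionnaire data depends on satisfaction at month 3 and on the choice that followed. Cross-over response could then be described in switchers, but with no concurrent non-switcher data on the primary instrument. A questionnaire missed at the final visit is also hard to recover. The window under which "in-person visits, check-ins, and questionnaires, can be rescheduled +/- 14 days within each of the outlined study timepoints" helps only if the site regards the questionnaire as due.

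**Working it through.** The plan states no figure on this point, so the check is an item-by-item comparison.

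**Inputs.** The nine columns of Table 2, and rows T1, T6, T7, T8 and T9 of Table 1. Three reading choices are needed: Table 2's baseline is matched to T1 (T0 lists only screening and enrolment); its 3-week follow-up is matched to T6; and the new treatment selection at T8 is counted as treatment preference.

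| Time point | Required by Table 2 | Listed in Table 1 | Missing from Table 1 |
|---|---|---|---|
| Baseline (T1) | 7 | 6 | treatment preference |
| 3 weeks (T6) | 4 | 3 | worksheet |
| 6 weeks (T7) | 4 | 3 | worksheet |
| 3 months (T8) | 9 | 8 | worksheet |
| 6 months (T9) | 9 | 3 | VISA-A, PROMIS-29, UWRI, patient goals, treatment preference, worksheet |
| Total | 33 | 23 | 10 |

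Required: 7 + 4 + 4 + 9 + 9 = 33. Listed: 6 + 3 + 3 + 8 + 3 = 23. Gaps: 33 − 23 = 10, of which 9 − 3 = 6 are at T9.

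**Which gaps are particular to T9.** The worksheet is missing from Table 1 at all 4 time points where Table 2 requires it, and treatment preference is also missing at T1. Those 4 + 2 = 6 gaps reflect general incompleteness in Table 1. The other 10 − 6 = 4 are VISA-A, PROMIS-29, UWRI and patient goals, one gap each, all at T9. Table 1 lists these four at every earlier visit where Table 2 requires them.

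**What a non-switcher would have.** For each of VISA-A, PROMIS-29 and UWRI, Table 2 gives 5 occasions (baseline, 3 weeks, 6 weeks, 3 months, 6 months). Table 1 gives 4 (T1, T6, T7, T8). After month 3 the count is 1 under Table 2 and 0 under Table 1.

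**What a switcher would have.** Under Table 1's Part 2 row, a switcher repeats the schedule above it, including the questionnaires. A 3-month visit counted from the month-3 switch falls at about 3 + 3 = 6 months, so switchers could have questionnaire values near month 6 even under Table 1.

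**Outcomes affected.** Section VI.c names six outcomes or groups of outcomes. Three (VISA-A, PROMIS-29, UWRI) are exposed. Ultrasound and functional tests appear at 6 months in both tables. The pain VAS is not a separate column or entry in either table and is outside this count.

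**The case against.** The best reply is that this is an omission in a summary table and not a real conflict. Table 1 outlines visits; Table 2 is presented as the list of assessments to be done in every arm and uses the language of requirement. T9 does not say that the questionnaires are not done. Table 1 is visibly incomplete elsewhere: it never lists the worksheet, and T0 names no instrument although eligibility depends on a baseline VISA-A below 80. Its silence is therefore weak evidence of intent. Section V.a also asks for VISA-A at each data collection point and treats month 6 as final data collection.

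Most of this stands as evidence of intent: Table 2 is the likelier plan, most clearly for VISA-A. It does not remove the conflict. The VISA-A sentence sits in the Part 1 text and does not mention PROMIS-29, UWRI or patient goals. The general incompleteness of Table 1 also does not explain why four items it otherwise lists whenever they are required disappear at one visit. A coordinator working from the visit-by-visit table would not see them as due.

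A reader might go further and infer that all 6-month questionnaires are lost, 60 × 3 = 180 completions under Table 2 against none, or that the Part 2 models would have no 6-month values at all. The documents do not support that. Zero describes the T9 cell only; switchers repeat the questionnaires under Table 1's own Part 2 row.

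**Conclusion.** The inconsistency is real and should be fixed, but its reach is limited. At 6 months Table 1 lists 3 of the 9 items in Table 2. Followed literally, it leaves non-switchers without VISA-A, PROMIS-29 or UWRI after month 3, so the repeated-measures models in Section VI.c would lack post-month-3 values of these outcomes for that group. The number of non-switchers cannot be known in advance, so no count of lost records is given.

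The conclusion is conditional on staff following Table 1, and the contrast with switchers assumes that the Part 2 row means repeating the questionnaires as well as the treatment visits. The T9 comparison itself does not depend on how baseline is matched between the tables.

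It would be wrong to infer that the randomised comparison is at risk: the 3-month assessments of these outcomes appear in both tables. The 6-month ultrasound, functional and satisfaction outcomes are likewise unaffected. Nor do the documents show that the 6-month questionnaires were dropped deliberately or will go uncollected.

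**What to change.** Align the T9 row of Table 1 with the 6-month row of Table 2 in all three columns, for switchers and non-switchers alike, by adding VISA-A (for each leg, in line with Section V.a), PROMIS-29, UWRI, patient goals, treatment preference and the return-to-sports worksheet. Add one sentence to Section V.b stating that Table 2 governs which assessments are due at each time point; this also covers the four gaps in Table 1 at earlier visits. Optionally, state in the Part 2 row which questionnaires switchers repeat.

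The cost is one table row and one sentence in an amendment, plus a few minutes of questionnaires per participant. No visit is added, because the 6-month visit is already held in person for ultrasound and functional testing.

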**Shockwave (SWT) Arm:**

The shockwave arm will receive shockwave treatment in addition to the physical therapy program from [name]. They will receive one treatment a week and one telephone check-in a week for three weeks. [name], the PI, will perform the SWT on all study participants, using the OrthoPlus Ultra 100/radial D-Actor. This Extracorporeal Pressure Activation Treatment (EPAT) device will be used at a radial shockwave of 3000 counts treatment settings of 15 Hz minimum 2 bars with a focus applicator head at mid-portion of Achilles using clinical focusing technique, and 3000 counts at 15 Hz minimum 2.5 bars using broad oscillator to myotendinous region and over symptomatic areas of gastrocnemius and soleus. Maximal settings will be 4 bars and initial treatment will start at 500 strikes at 1.5 bars for each treatment head to allow participant to be comfortable as we start shockwave sessions. The research coordinator will conduct the telephone calls to check-in on physical therapy exercise compliance and response to each treatment.

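### The +/-14-day allowance lets the 3-week and 6-week assessment windows overlap (by 8 days if they are days 21 and 42) and lets the 3-week questionnaires precede most of the treatment course

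*Combined protocol and SAP*

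**What the plan says.** - **Window.** The note under Table 1 in V.b Visit Details begins "Due to the nature of COVID-19" and then states that visits, check-ins and questionnaires "can be rescheduled +/- 14 days within each of the outlined study timepoints". The width is the same at every time point. The note gives no end date, no condition for using the allowance and no minimum gap between assessments.
- **Early assessments.** VISA-A, ProMIS-29 and UWRI are collected at "T6: week 3 visit 2" and again at "T7: 6 week follow up" (Table 1). Table 2 labels the first of these "3-week follow-up". In the physical therapy and shockwave arms the T6 entry is "telephone check-in VISA-A, ProMIS-29, UWRI". In the combination arm T6 is also the last PBMT session. T7 is a telephone contact in all three arms.
- **Treatment course.** For the shockwave arm: "They will receive one treatment a week and one telephone check-in a week for three weeks". The combination arm has PBMT twice weekly and SWT once weekly over the same three weeks.
- **Analysis.** VI.c Statistical methods names VISA-A as the primary outcome without a time point. It has no rule for assigning a score to a time point and no use of the actual assessment date.

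**The concern.** Two assessments meant to describe the early course should have windows that cannot be confused, and the one placed at the end of the treatment weeks should not be obtainable before those weeks are over. Neither is assured here. A single allowance, wide enough for visits three months apart, is also applied to questionnaires about three weeks apart and to sessions one week apart or less.

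At stake is the meaning of the 3-week and 6-week scores. A score from the shared days could carry either label. A 3-week score from early in its window would describe response to a fraction of the course. In a pilot with 20 runners per arm, the early course of VISA-A is a useful product of the study, and a few mistimed scores would be a visible share of each arm.

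**Working it through.** The plan gives no figure to reproduce on this point; the check is interval arithmetic on its own schedule.

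**Inputs**
- Half-width w = 14 days (note under Table 1).
- 3-week assessment: day 21 if Table 2 is read literally; day 15-18 if Table 1's second visit of week 3 is placed early or midway in that week. The day is not stated, so both are assumptions.
- 6-week assessment: day 42 from T1 (assumption; no anchor is stated).
- Sessions, with T1 as day 0: SWT on days 0, 7 and 14. PBMT on days 0, 3, 7, 10, 14 and 17, one nominal layout of twice a week.

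**Overlap.** For nominal days a < b the windows are a +/- w and b +/- w. They share (a + w) - (b - w) + 1 = 2w + 1 - (b - a) days when that is positive.

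| 3-week day | 6-week day | Windows | Shared days |
|---|---|---|---|
| 21 | 42 | 7-35 and 28-56 | 29 - 21 = 8 (days 28-35) |
| 18 | 42 | 4-32 and 28-56 | 29 - 24 = 5 |
| 17 | 42 | 3-31 and 28-56 | 29 - 25 = 4 |
| 15 | 42 | 1-29 and 28-56 | 29 - 27 = 2 |
| 21 | 63 (6 weeks counted from the end of treatment) | 7-35 and 49-77 | none |

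The last row is the only reading examined that removes the overlap. Table 2 runs 3-week, 6-week, 3-month, 6-month, which reads more naturally as counting from one start.

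**Half-width that removes the overlap.** At days 21 and 42 the windows are disjoint when 2w + 1 <= 21, that is w <= 10. At w = 11 they share 2 days. At w = 7 they are days 14-28 and 35-49.

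**Sessions given before the earliest permitted 3-week score**, with sessions on their nominal days:
- T6 at day 21: earliest day 21 - 14 = 7. Before that day, 1 of 3 SWT and 2 of 6 PBMT sessions (2 of 3 and 3 of 6 if same-day sessions count).
- T6 at day 17: earliest day 3. Before that day, 1 of 3 SWT and 1 of 6 PBMT sessions (2 of 6 PBMT if the same day counts).

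**Later visits.** 3 months: 91 +/- 14 = days 77-105 (or 84 +/- 14 = 70-98). 6 months: 182 +/- 14 = days 168-196. Neither window meets the 6-week window, which ends on day 56, and they do not meet each other.

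**Session spacing.** Weekly SWT sessions are 7 days apart and PBMT sessions closer still. A move of up to 14 days either way exceeds that spacing, so the note and the frequencies in the two treatment-arm sections cannot both hold as written.

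**The case against.** The best case against has four parts.

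1. *The overlap is at the edges.* Nominal dates stay about three weeks apart, and the allowance is for COVID-19 rescheduling, not routine practice. This stands as a limit on how often the problem would arise. A reader might infer that the two assessments are in effect one; the documents do not support that. They support only that a score from the shared days could be assigned to either.
2. *A day-7 questionnaire is unlikely.* Visits are numbered in order, T6 follows the third SWT session, and in the combination arm it is itself a session. Disruption would more plausibly delay than advance a visit. That is fair as to likelihood. But the note lists questionnaires separately from visits, and nothing requires the T6 set to follow the week-3 contact.
3. *A wide questionnaire window may be sensible.* If sessions slip, moving the questionnaire with them keeps it after treatment. So the fact that many of these contacts are by telephone does not by itself show the allowance to be unjustified. This stands, and it favours an ordering rule.
4. *The effect on the trial's comparison is unproven.* A reader might infer a biased primary result, since VISA-A is the primary outcome and the device arms have more in-person sessions to reschedule. Such a bias would be roughly the weekly change in VISA-A multiplied by the difference between arms in mean assessment time, in weeks. The documents give neither quantity, and no standard deviation or relevant difference to judge it against. Unequal rescheduling is possible but not shown.

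**Conclusion.** The concern holds as a moderate weakness that is cheap to repair. As written, the plan permits the 3-week and 6-week windows to share 8 days when the assessments are days 21 and 42 from T1, or 2-5 days when T6 is day 15-18. It also permits a 3-week VISA-A before most of the treatment course. Both results rest on assumed nominal days, because no anchor is stated; counting 6 weeks from the end of treatment would remove the overlap but is the less natural reading.

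The reach is limited to the 3-week and 6-week results. The 3-month assessment that closes Part 1 is untouched by the overlap. VI.c does not name a primary time point, but that silence does not justify saying that the main randomised comparison is compromised. The conflict between the allowance and the session frequencies is a separate inconsistency that needs reconciling.

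**What to change.** 1. State the anchor day (for example T1 = day 0) and the nominal day of the 3-week and 6-week assessments.
2. Give those two questionnaire sets narrower windows that do not overlap, with remote completion allowed. +/-7 days is one choice; at days 21 and 42 any half-width up to 10 days works. The +/-14 days can stay for the 3-month and 6-month visits.
3. Require the 3-week questionnaires to be completed no earlier than the T6 contact and before the 6-week window opens. With +/-7 days at days 21 and 42, the part of days 14-28 before T6 is then unavailable. If T6 slips so far that both conditions cannot be met, keep the score and treat it as outside its window.
4. Record the actual completion date, and in VI.c use time since T1 in the analysis of any score outside its window.
5. Reconcile the allowance with the session frequencies in the Shockwave (SWT) Arm and SHW and PBMT Arm sections. How that is resolved is a clinical decision for the investigators.

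The cost is a short amendment to the note under Table 1, a line in VI.c and a date field on the questionnaires. The downside is that a few questionnaires will fall outside the narrower windows, but they remain usable through their actual date.
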